Title: Co-Developing and Piloting Culturally-Responsive Informational Materials About Autism for Families of Young Children: Employing a Train-the-Trainer Implementation Model Within a Nonprofit Setting

NCT number: NCT06314438

Date: 3/6/2025

Study Protocol

Background:

Access to early, evidence-based autism-specific treatment can profoundly improve long-term outcomes for children with Autism Spectrum Disorder (ASD). However, current estimates reveal an eight-month to three-year gap between caregiver first concerns about their child's ASD-related behaviors and receipt of ASD-specific services. This prolonged time-period between caregiver first concerns and receipt of ASD-specific services is characterized by elevated parenting stress, increased child behavioral challenges, and reduced quality of life, even compared to families of children with non-ASD developmental concerns. Unfortunately, culturally and linguistically diverse (CLD) communities experience lengthier time-periods between first concerns and receipt of services, report increased difficulty accessing timely diagnostic and treatment services, and ultimately experience worse health outcomes compared to White communities.

Objectives:

The investigators partnered with Mother Africa, a local non-profit organization, to 1) co-design culturally-responsive caregiver-focused educational materials to support CLD families with young children who have social communication delays or ASD and 2) develop a novel route for dissemination of information and materials within non-profit organizations, which are often the preferred entry-point for accessing healthcare information and services for underserved populations, rather than traditional medical facilities. The educational materials aim to support caregiver and child well-being by increasing caregiver knowledge and use of ASD specific parenting strategies as well as increasing caregiver awareness and use of local ASD resources. This research has the potential to effect programmatic changes in the services and settings available to support CALD communities during the early years of a child's ASD condition and thereby improve child and caregiver outcomes.

Methods/Design:

Participants included 6 non-specialist providers working at a local non-profit organization and 35 caregivers. Caregivers were affiliated with the non-profit organization and met the following inclusion criteria: has a child who screened at likelihood on the Ages and Stages Questionnaire; and speaks one of the following languages: Arabic, Mai Mai, Swahili, French, Tigrinya, Dari.

This project utilized a three-stage development and implementation process informed by the literature on bridging cultural adaptation with implementation science to ensure that our end-product (i.e., culturally-responsive caregiver education materials) is relevant for consumers and feasible for deployment. Co-design methods (e.g., treating community members as equal collaborators in the design process, synthesizing feedback from target users into actionable insights) were used to ensure that caregivers, ASD specialists, service providers, and program supervisors are actively involved in the design of the curriculum and its implementation needs.

Stage 1: For the co-design phase, a working group of caregivers, Mother Africa supervisors (i.e., program managers), Mother Africa providers (i.e., administrators of developmental screeners who are matched to the culture and language of their clients), and ASD specialists were assembled and met to culturally adapt existing caregiver-education materials for a total of eight co-design sessions over 6 months. Stage 2: Using a web-based tutorial, Mother Africa staff were taught to deploy the

culturally-adapted curriculum. **Stage 3:** Providers piloted the curriculum to groups of caregivers. Supervisors, providers, and caregivers completed self-report surveys during Stages 2 and 3 to provide feedback on the cultural adaptation, implementation, and caregiver and child outcomes. The current study registered on clinicaltrials.gov focuses only on this third stage of our project (i.e., the pilot feasibility trial).

Statistical Analysis Plan:

The primary goal of our analyses was to measure change in caregiver knowledge and service usage before and after participating in our program. As such, paired samples T-tests were used to test for differences before and after implementation of the Family Care Project on the following dimensions: Staff Competence in Assisting Families with Children at-autism Likelihood Survey (self-report); The Maternal Self-Efficacy Scale Questionnaire; and Caregiver Knowledge and Use of Behaviors that Support Children at autism-likelihood Survey.

Additional, secondary surveys were analyzed using descriptive statistics for Likert scale measures and those using discrete variables (i.e., received/not received), including Staff Competence in Assisting Families with Children at-autism Likelihood Survey (self-report), The Maternal Self-Efficacy Scale Questionnaire, Caregiver Knowledge and Use of Behaviors that Support Children at autism-likelihood Survey, Current Services Utilized by Families to Support Children at autism-likelihood Survey, and Family Care Project Feedback Survey of Implementation Properties. All surveys except one were analysed using mean and standard deviation. Current Services Utilized by Families to Support Children at autism-likelihood Survey was operationalized as number of families who received or did not receive diagnostic and intervention services before and after implementation of the Family Care Project.

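### Service usage is half of the stated primary goal, but it gets only before/after family counts, with no paired analysis and no measure of precision

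*Combined protocol and SAP*

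**What the plan says.** The Statistical Analysis Plan opens with the goal: "The primary goal of our analyses was to measure change in caregiver knowledge and service usage before and after participating in our program". The Objectives section supports this: the materials are meant to raise caregiver knowledge and use of parenting strategies "as well as increasing caregiver awareness and use of local ASD resources".

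The next sentence of the SAP presents the tests as a consequence of the goal: "As such, paired samples T-tests were used to test for differences before and after implementation of the Family Care Project on the following dimensions". Three surveys follow. The list begins "Staff Competence in Assisting Families with Children at-autism Likelihood Survey (self-report); The Maternal Self-Efficacy Scale Questionnaire" and ends with the survey of caregiver knowledge and use of supportive behaviors. The services survey is not listed.

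That survey appears only in the second paragraph of the SAP, which opens: "Additional, secondary surveys were analyzed using descriptive statistics for Likert scale measures and those using discrete variables (i.e., received/not received". It is the one survey not summarised by mean and standard deviation. Instead it is "operationalized as number of families who received or did not receive diagnostic and intervention services before and after implementation of the Family Care Project".

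On size, Methods/Design says: "Participants included 6 non-specialist providers working at a local non-profit organization and 35 caregivers".

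**The concern.** The goal has two parts, and only caregiver knowledge receives an inferential analysis. Staff competence and maternal self-efficacy, which the goal does not name, are tested. Service usage, which it does name, is not. The survey of caregiver behaviors does not fill the gap, because it concerns what caregivers do with the child and not which services the family receives.

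Numbers of families receiving services before and after give a net change if the same families are counted both times. They do not show how precisely that change is estimated. For paired yes/no data, precision depends on how many families gained a service and how many lost one. Whether the two totals reveal this depends on what *received* means:

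- **Ever received (cumulative).** No family can lose the status, so the totals fix the whole before-by-after table.
- **Receiving now (current).** The totals fit many tables, and the paired interval or test cannot be recovered from them.

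The plan does not say which meaning applies. The survey's name points to current use and the coding points to receipt. Under either meaning no interval or test is planned. A reader would therefore get a change in numbers of families with no indication of whether 35 caregivers are enough to support it.

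**Working it through.** **Stated figures.** The documents give no service-use rate, hypothesis, alpha or sample-size calculation, so there is no figure of the plan's own to reproduce. The textual claim rests on the comparison above. The arithmetic below only shows how much the missing information can matter.

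**Inputs.** n = 35 caregivers is from Methods/Design. Assumed: one caregiver per family, all 35 linked, 10 families receiving services before and 16 after.

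**Formulas.** Let b = families that gained a service and c = families that lost one.

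- Net change: D = (b - c)/n = 6/35 = 0.171, the same for every split.
- Feasible splits: b = c + 6, with c from 0 to min(10, 35 - 16) = 10.
- Exact McNemar: two-sided binomial on b + c pairs with probability 0.5.
- Wald: SE = sqrt[(b + c) - (b - c)²/n]/n.
- Newcombe paired interval: lower limit = D - sqrt(x² - 2φxy + y²). Here x is the distance from the after proportion to its lower Wilson limit, y the distance from the before proportion to its upper Wilson limit, and φ the within-pair correlation. The upper limit is the mirror image. φ is continuity-corrected: n/2 is taken off the cross-product when that is positive.

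**Worked example, 6 gained and 0 lost.** The table has 10 families with services both times, 6 gained, 0 lost and 19 with neither.

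- McNemar p = 2 × 0.5⁶ = 0.031.
- Wald SE = sqrt(6 - 36/35)/35 = 0.0637.
- Wilson limits: after 16/35, 0.305 to 0.618; before 10/35, 0.163 to 0.451.
- φ = (10×19 - 17.5)/sqrt(16×19×10×25) = 172.5/275.7 = 0.626.
- Newcombe lower limit = 0.1714 - sqrt(0.1524² - 2×0.626×0.1524×0.1648 + 0.1648²) = 0.1714 - 0.1377 = 0.034.

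**Results, n = 35, net change +17.1 points throughout**

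| Gained / lost | Exact McNemar p | Newcombe 95% CI (points) | Wald SE | Wald 95% CI (points) |
|---|---|---|---|---|
| 6 / 0 (only table possible if cumulative) | 0.031 | +3.4 to +29.9 | 0.0637 | +4.7 to +29.6 |
| 8 / 2 | 0.109 | -0.7 to +33.3 | 0.0856 | +0.4 to +33.9 |
| 16 / 10 (arithmetical extreme) | 0.327 | -11.1 to +42.4 | 0.1428 | -10.8 to +45.1 |

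The standard error at the extreme is 0.1428/0.0637 = 2.2 times that with no losses.

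**Reader with totals only.** Treating 10/35 and 16/35 as independent, SE = sqrt(0.286×0.714/35 + 0.457×0.543/35) = 0.1137. The interval is -5.1 to +39.4 points (Fisher p = 0.22) whichever row is true.

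**Fewer linked pairs.** Assume 28 pairs, 8 before and 14 after, net 6/28 = +21.4 points. Newcombe intervals are +4.5 to +36.4 for 6/0 (p = 0.031), -0.7 to +40.6 for 8/2 (p = 0.109) and -11.0 to +49.2 for 14/8 (p = 0.286).

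**Sensitivity to the interval method.** Without the continuity correction in φ, the 8/2 lower limit moves to about +0.2 points at n = 35 and +0.4 at n = 28. That row is therefore borderline and should not be read as clearly unsupported. The spread between rows remains.

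**Smallest gains giving exact p < 0.05.** 6 with none lost, 8 with one lost (p = 0.039), 10 with two lost (p = 0.039).

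**The case against.** The strongest reply is that this is a small pilot feasibility study whose goal is to measure change, not to test a hypothesis. Counts do measure net change, and the plan does give this survey an explicit descriptive analysis. No decision rule depends on a test of service use. That limits the seriousness of the point but does not remove it. The plan itself calls this change primary and tests other measures under the same goal, and an interval suits a pilot better than a bare count.

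A paired t-test is not the natural method for a yes/no outcome, so leaving the survey off the t-test list is understandable. I accept that. The gap is that nothing suited to paired binary data takes its place.

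The plan names no confidence interval for any outcome. That is also true, but the three tested surveys at least get a paired test with mean and standard deviation.

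The illustration uses assumed counts, and its last row requires every family with services at baseline to lose them, which is a bound and not a likely result. Under cumulative receipt, a reader who knew that, and knew the same families were counted twice, could rebuild the 6/0 table. The plan tells the reader neither.

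**Conclusion.** The concern holds. Change in service usage belongs to the stated primary goal, is missing from the tests said to follow from it, is handled with the secondary surveys, and is to be reported without any statement of precision. Nothing else in the documents fills the gap.

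Its size cannot be stated for this trial, because no service counts are given. Under the assumed 10-to-16 rise in 35 linked families, one pair of totals is compatible with paired intervals from about +3 to +30 points up to -11 to +42 points. The wide end needs the current-use meaning and extreme turnover. With cumulative receipt only the narrow interval applies, and the loss is that it goes unreported. The conclusion about the text does not depend on these assumptions. This should be fixed, but it is a reporting weakness in an uncontrolled pilot and does not invalidate the study.

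**What to change.** 1. For families with both surveys, cross-tabulate before by after, separately for diagnostic and for intervention services. Report the number of pairs, the numbers gained, lost and unchanged, and the paired difference in proportions with a 95% interval suited to small samples. The Newcombe paired interval is one choice; state the version used. Give exact McNemar as supportive.
2. State whether receipt is cumulative or current.
3. Optionally add new receipt among families without the service at baseline, as a supplementary estimate.
4. Describe the result as uncontrolled before/after change. The SAP is written in the past tense, so an added analysis is probably post hoc. Label it so if the data had been seen.

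If responses to this survey cannot be linked by family, say so and restate service usage as a descriptive secondary aim, so that the goal and the analysis agree.

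The cost is some SAP wording and one extra table, with no new data collection. The planned t-tests already need before/after linkage for the caregiver surveys, but the documents do not confirm it for this one. The interval will be wide, and the report should say so.

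### The t-tests placed under a caregiver-only primary goal include a staff survey with about 6 pairs, and all three tested surveys are then relabelled secondary

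*Combined protocol and SAP*

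**What the plan says.** The Statistical Analysis Plan opens with its aim: "The primary goal of our analyses was to measure change in caregiver knowledge and service usage before and after participating in our program". As a consequence of that aim it states that "paired samples T-tests were used to test for differences before and after implementation of the Family Care Project on the following dimensions: Staff Competence", and then adds the Maternal Self-Efficacy Scale and the Caregiver Knowledge and Use of Behaviors survey.

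Its second paragraph turns to further surveys: "secondary surveys were analyzed using descriptive statistics for Likert scale measures and those using discrete variables (i.e., received/not received), including Staff Competence". The list continues with "The Maternal Self-Efficacy Scale Questionnaire, Caregiver Knowledge and Use of Behaviors that Support Children at autism-likelihood Survey, Current Services Utilized by Families" and ends with a feedback survey. All three t-tested surveys are therefore named again. The same paragraph says that every survey but one is summarised by mean and SD. The exception is Current Services, which "was operationalized as number of families who received or did not receive diagnostic and intervention services before and after implementation". No test or paired analysis is named for it.

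On numbers, Methods/Design says: "Participants included 6 non-specialist providers working at a local non-profit organization and 35 caregivers". It also says: "Supervisors, providers, and caregivers completed self-report surveys during Stages 2 and 3". The number of supervisors is not given, nor is it stated who answered the staff survey. Under Objectives, the materials are meant to benefit the well-being of caregivers and children. The stated means are these: "increasing caregiver knowledge and use of ASD specific parenting strategies as well as increasing caregiver awareness and use of local ASD resources". A second objective is dissemination through non-profit organisations. The title names a train-the-trainer model.

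**The concern.** The status of a survey decides which result answers the primary goal. Here the goal sentence, the list of tests and the list of secondary surveys give different answers.

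Two consequences follow. First, a staff p-value reported under a caregiver goal can be taken as evidence on that goal although no caregiver contributed to it. Meanwhile service usage, which the goal names, has only a secondary place and a pair of counts. Second, the staff test rests on very few people. A non-significant result could be read as showing that training left staff competence unchanged, which so few pairs cannot show.

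**Working it through.** **Step 1: set the goal against the labels.** All entries are from the Statistical Analysis Plan.

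| Survey | Named in the primary goal? | t-test under that goal? | Listed as secondary? |
|---|---|---|---|
| Caregiver Knowledge and Use | Yes (knowledge) | Yes | Yes |
| Maternal Self-Efficacy | No | Yes | Yes |
| Staff Competence | No (staff self-report) | Yes | Yes |
| Current Services | Yes (service usage) | No | Yes |

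One of the three tested surveys matches the goal by name, and all three also carry the secondary label. Of the two surveys that match the goal, one is not tested. Reporting both a t-test and a mean with SD for one survey is no conflict. The conflict lies in the status.

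**Step 2: precision of the staff test.** The plan gives no power, significance level, SD or expected effect, so there is no figure to reproduce. Inputs:
- 6 providers and 35 caregivers, from Methods/Design, taken as complete pairs.
- Two-sided 5% level: assumed.
- 5 pairs (one provider missing) and 8, 9 or 10 pairs (two to four supervisors also answering): assumed, to show the range.

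Effects are in SDs of the change score, d = mean change / SD of change.
- CI half-width = t(0.975, n−1)/√n. For n=6: 2.571/2.449 = 1.05.
- Power is from the noncentral t distribution with n−1 degrees of freedom and noncentrality d√n.
- For an observed d=0.8: t = 0.8√n. For n=6: 0.8 × 2.449 = 1.96 on 5 degrees of freedom, p=0.107.

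| Pairs | Change for 80% power | 95% CI half-width | Power at 0.5 SD | p if 0.8 SD observed | 95% CI for that result |
|---|---|---|---|---|---|
| 5 | 1.68 | 1.24 | 14% | 0.148 | −0.44 to 2.04 |
| 6 | 1.43 | 1.05 | 17% | 0.107 | −0.25 to 1.85 |
| 8 | 1.16 | 0.84 | 23% | 0.058 | −0.04 to 1.64 |
| 9 | 1.07 | 0.77 | 26% | 0.043 | 0.03 to 1.57 |
| 10 | 1.00 | 0.72 | 29% | 0.032 | 0.09 to 1.52 |
| 35 (caregivers) | 0.49 | 0.34 | 82% | – | – |

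With 6 pairs the staff interval is about three times as wide as a caregiver interval (1.05/0.34 = 3.1).

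**Step 3: what the number of pairs changes.** In this example the result crosses 5% between 8 and 9 pairs, so three supervisor responses are enough to reverse its significance. Imprecision persists across the staff range: even with 10 pairs, power for a 0.5 SD change is 29%.

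**The case against.** **The second paragraph is only a loosely worded list of summaries.** It covers every named survey and says how each is summarised. That reading is plausible, but the secondary label is attached to the surveys, not to the summaries. Even on that reading, a staff measure is still tested under a caregiver goal, and service usage still appears only among the secondary surveys.

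**Staff competence and self-efficacy belong in this project.** This stands. The title and the dissemination objective justify measuring staff. Self-efficacy can reasonably be seen as serving the well-being aim in Objectives. A reader might infer that these two surveys should not have been tested at all; the documents do not support that. What they support is narrower: neither survey answers the primary goal as written.

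**A reader can tell which survey fits the goal.** This also stands in part. One might infer that the primary result cannot be identified, but caregiver knowledge matches by name. The difficulty is that the plan then calls that survey secondary as well.

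**The power figures are hypothetical.** This is a pilot feasibility trial. The plan makes no power claim and nowhere says that a non-significant staff result would mean no change. The figures therefore show how the staff result should be read; they do not show a broken promise, and the labelling conflict does not depend on them. Nor should one infer that a few supervisor responses would be immaterial, as Step 3 shows.

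**The registration may already fix the outcomes.** Methods/Design says that the study is registered, and the record is not part of these documents. That is a reason to check it before relabelling.

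**Conclusion.** The concern holds as a conflict between the stated goal and the labels. One of three t-tested surveys matches the primary goal by name, all three are also called secondary, and service usage is only in the secondary list. This rests on the text alone.

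The staff test is very imprecise. With 6 pairs and an assumed two-sided 5% level, 80% power requires 1.43 SD and the CI half-width is 1.05 SD. The count of 6 is inferred from the number of providers. Whether a given gain reaches significance depends on how many supervisors answered, which is not stated.

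The plan is written in the past tense, and a reader might infer that statuses were chosen after the results were seen. Nothing in the documents shows that. This is a wording and reporting correction for a small pilot, worth making because it is cheap and settles which results answer the goal.

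**What to change.** 1. Give each survey one status and use it in both paragraphs. Follow the written goal, reconcile the labels with the registered outcomes, and date the change.
2. Place Caregiver Knowledge and Use and Current Services under the primary goal. Report Current Services as paired change within families: how many gained a service, how many lost one, and how many stayed the same. Separate before and after counts give only the net difference.
3. Label Staff Competence secondary and say that it is not evidence on the caregiver goal. Label Maternal Self-Efficacy secondary unless the registered outcomes say otherwise.
4. State that the means and SDs in the second paragraph are summaries and do not give a survey a second status.
5. For staff, report the mean change with its 95% CI, the number of pairs, and whether supervisors are included. The t-test may stay, but a non-significant p-value should not be reported as no change. Individual staff scores need not be published; a handful of staff at a named organisation could be identified.

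The cost is a few sentences, one interval, a count of pairs and one cross-tabulation. No new data are needed, provided each family's before and after service answers can be linked. The real downside is that the staff and self-efficacy results can no longer be offered in support of the primary goal.

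### Service usage is read from two uncontrolled before/after counts; some uptake is expected with elapsed time alone, so a rise cannot be read as a program effect

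*Combined protocol and SAP*

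**What the plan says.** The Statistical Analysis Plan opens with its aim: "The primary goal of our analyses was to measure change in caregiver knowledge and service usage before and after participating in our program". Service usage is thus one of two named components, beside caregiver knowledge.

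The plan does not include the services survey among the paired t-tests. It places it in the second paragraph: "Additional, secondary surveys were analyzed using descriptive statistics for Likert scale measures and those using discrete variables (i.e., received/not received". The outcome is "operationalized as number of families who received or did not receive diagnostic and intervention services before and after implementation of the Family Care Project". That gives two totals, one before and one after, with no test and no interval estimate.

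Methods/Design describes the registered part as follows: "The current study registered on clinicaltrials.gov focuses only on this third stage of our project (i.e., the pilot feasibility trial". No concurrent, wait-list or historical comparison appears. The sample is given as "Participants included 6 non-specialist providers working at a local non-profit organization and 35 caregivers", and the number of families is not stated separately. One entry criterion is that the caregiver "has a child who screened at likelihood on the Ages and Stages Questionnaire"; the other concerns language. Nothing is said about diagnosis or services already received.

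The Background supplies the natural history: "current estimates reveal an eight-month to three-year gap between caregiver first concerns about their child's ASD-related behaviors and receipt of ASD-specific services". It adds that "culturally and linguistically diverse (CLD) communities experience lengthier time-periods between first concerns and receipt of services".

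**The concern.** Families enter after a positive screen, which puts them on a path that leads some of them to evaluation and intervention without any program. A count taken later in the same families will include whatever uptake would have happened anyway, and the design gives no means of separating the two.

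The count is also ambiguous. If *received* means ever received, status cannot reverse and the later count in the same families cannot be lower. If it means receiving now, as the survey's title suggests, a family whose diagnostic evaluation ended before the program could move to *not received*. On either reading, families already served at baseline cannot newly gain but remain in the total. Two marginal totals also hide who changed: no net change fits both no movement at all and equal numbers starting and stopping.

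At stake is the Objectives' aim of increasing use of local resources. A higher count afterwards is easily read as meeting that aim, and nothing in the plan guards against that reading.

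**Working it through.** The documents give no service rate, sample-size calculation or significance level, so there is no planned figure to reproduce. The calculation below only shows how much the count could move if the program did nothing.

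**Inputs from the documents**
- 35 caregivers (Methods/Design), taken as at most 35 families.
- A gap of 8 to 36 months from the time a caregiver becomes worried to services (Background).
- A longer gap in the study's communities (Background, not quantified).

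**Assumptions, not in the documents**
- The gap is read as a mean wait *m* with constant hazard. A value of 48 months is added as a sensitivity value for the longer gap.
- The interval *t* is 1, 3 or 6 months.
- Either no family or half of them are already served, leaving *n* = 35 or 18 at risk (35 × 0.5 = 17.5, rounded).

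**Cumulative reading, zero program effect**

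The probability that a family newly receives a service is p = 1 − exp(−t/m). Expected new recipients are n × p. The probability that the count rises at all is 1 − (1 − p)^n = 1 − exp(−n·t/m).

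Example with t = 3, m = 36, n = 35: p = 1 − exp(−0.0833) = 0.080; expected 35 × 0.080 = 2.8; P(any rise) = 1 − exp(−2.917) = 0.946.

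Each cell gives expected new recipients; P(any rise).

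| Interval | At risk | m = 8 | m = 36 | m = 48 |
|---|---|---|---|---|
| 1 month | 35 | 4.1; 0.987 | 1.0; 0.622 | 0.7; 0.518 |
| 1 month | 18 | 2.1; 0.895 | 0.5; 0.393 | 0.4; 0.313 |
| 3 months | 35 | 10.9; >0.999 | 2.8; 0.946 | 2.1; 0.888 |
| 3 months | 18 | 5.6; 0.999 | 1.4; 0.777 | 1.1; 0.675 |
| 6 months | 35 | 18.5; >0.999 | 5.4; 0.997 | 4.1; 0.987 |
| 6 months | 18 | 9.5; >0.999 | 2.8; 0.950 | 2.1; 0.895 |

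Replacing p by t/m (a uniform wait) gives similar or larger values.

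**Current-use reading**

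Families can now also leave services. Assume 10 families receiving and 25 not, with independent gains and losses.
- 3% gain and 3% loss: expected net change 25 × 0.03 − 10 × 0.03 = 0.45; P(net rise) = 0.43.
- 8% gain and 8% loss: expected net change 25 × 0.08 − 10 × 0.08 = 1.2; P(net rise) = 0.66.

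The expected change is upward in both cases, because more families can start than can stop, but a net rise is far from assured.

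**The case against.** The strongest reply is that this is a pilot, that the survey is listed as secondary and described only, and that the plan speaks of measuring change without claiming causation. All of that is correct. It rules out one stronger inference a reader might draw, that the false-positive rate is inflated: no test or significance level is attached to this outcome. It does not settle interpretation, because the same plan puts change in service usage in its primary goal and nowhere limits what a change may be taken to mean.

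A second reply is that the illustration rests on borrowed inputs. This also stands. The Background's gap runs from the time a caregiver becomes worried to ASD-specific services, not from enrolment to any service on the survey. Families may already be part-way through the wait. The study's communities wait longer, and some children who screen positive may never need ASD-specific services. These considerations pull in different directions, so the table shows possible size only. For the same reason the 8-to-36-month gap is unsuitable as a benchmark for the observed result: it has the wrong time origin and is too wide to discriminate.

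A third reply is that restricting to families unserved at baseline also yields a quantity that can only be zero or positive. True. That proportion describes uptake over an interval; it does not remove the confounding with time. It is an improvement only when shown with the families who stopped and with a limited conclusion.

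**Conclusion.** The point holds as a limit on interpretation. Some uptake is expected from elapsed time alone, so a rise in the count cannot be attributed to the program.

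A reader might go further and infer that the count is bound to rise even under a useless program. The documents do not support that. The outcome depends on three things they leave unstated: the before-to-after interval, the share already served, and whether receipt is ever or current. On the cumulative reading with waits of 8 to 36 months and at least 3 months between surveys, the chance of a rise is 0.78 or more even with half already served. With a 1-month interval and half already served, it falls to 0.39 at a 36-month wait and 0.31 at the assumed 48 months. Under current use it can be below one half (0.43 in one scenario).

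That service usage sits in the primary goal while its survey is listed as secondary is a separate inconsistency, not argued here.

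**What to change.** Make these changes separately for diagnostic and for intervention services:

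1. Fix one meaning of *received* (ever, or at the time of the survey) and apply it at both time points.
2. Replace the two counts with a per-family table of transitions: newly received, stopped, continued, never.
3. Report newly received as a fraction of families not served at baseline, with an exact 95% CI. List families already served at baseline separately.
4. Give the interval between the before and after surveys.
5. State that this outcome, and the paired t-test outcomes from the same single-group design, show uncontrolled change and do not estimate a program effect.

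No control arm or new data collection is needed if the before and after surveys can be linked by family. The paired t-tests imply such linkage for other measures, but the documents do not confirm it for this survey. Because the plan is written in the past tense, the new table should be labelled as specified after the fact. The cost is SAP wording and one re-tabulation, with a smaller denominator and a more cautious conclusion.
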